The chosen study sample size and randomization allocation will also provide acceptable power levels for the comparison of different combination regimens, ie, JNJ-3989+JNJ-6379+NA (Arm 1, 100-mg dose of JNJ-3989) versus JNJ-3989+NA (Arm 3, 100-mg dose of JNJ-3989), and versus JNJ-6379+NA (Arm 5), respectively (Table 7). Based on the min test approach, Table 7 shows that the power levels vary depending on both the rate difference between Arm 1 and Arm 3 and the assumed rate for Arm 5. For example, for the same delta of 25% between Arm 1 and Arm 3 and between Arm 1 and Arm 5, the power to conclude that Arm 1 is statistically superior to Arm 3 and Arm 5 is 87%, assuming a response rate of 25% in both Arm 3 and 5.

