Each of the dose-response shapes in the candidate set will be tested using the corresponding contrast t-test statistic, employing a critical value derived for the maximum of the t-test statistics (based on the associated multivariate t-distribution) to ensure appropriate multiplicity correction that preserves the one-sided Type I error rate at 0.05. A dose-response trend is established when the maximum of the t-test statistics exceeds the critical value.

After establishing a significant dose-response signal, the testing procedures continue with the comparison of the percentage of participants who completed the 48-week study intervention and

qualified for stopping NA treatment in Arms 1 and 5 against control Arm 6, respectively. The Mantel-Haenszel (MH) test will be used in the pairwise comparisons at a one-sided alpha level of 0.05 adjusting for the randomization stratification factors of screening HBeAg status and treatment history. The Wilson test will be used at a one-sided alpha level of 0.05 with no adjustment for stratification factors as a secondary analysis.

The testing among the regimens (Arm 1 vs. Arm 3, and Arm 1 vs. Arm 5) will be performed using the min test approach. The JNJ-3989+JNJ-6379+NA (Arm 1) combination regimen will be declared statistically superior to the dual regimens (Arm 3 and 5) if both tests of Arm 1 vs Arm 3 and Arm 1 vs Arm 5 demonstrate statistical significance at the one-sided 0.05 level. The MH test for the difference of 2 proportions adjusted for the 2 randomization stratification factors will be applied to all pairwise comparisons.

As a secondary analysis, the primary efficacy endpoint will be compared between intervention arms in a logistic regression model with factors for treatment arm, treatment status and HBeAg status at screening. The potential impact of each intervention-by-randomization factor interaction will be assessed by comparing the model with and without interaction terms. Appropriate 90% CIs will be also calculated without multiplicity adjustment. Exploratory subgroup summaries will be displayed graphically in forest plots.

9.4.1.2. Key Secondary Efficacy Endpoint of Functional Cure at Week 72 (HBsAg Seroclearance 24 Weeks After Completion of All Study Intervention at Week 48)

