1.4. Sample Size Justification

The total study sample size is 450 participants with a 2:2:2:2:1:1 randomization ratio, where 90 participants will be randomly allocated to each of the arms including a JNJ-3989 dose (Arms 1 to 4) and 45 participants will be randomly assigned to each of the arms with no JNJ-3989 component (Arms 5 and 6). Due to the global impact of the pandemic Coronavirus Disease 2019 (COVID-19) and the use of the modified ITT analysis set as primary set for the efficacy analyses, study enrollment was extended by approximately 5% of participants.

Statistical power to test a dose-response signal (max trend test) was assessed using the generalized version of the MCP-Mod ([Pinheiro J. et al., 2014](#)) applied to the binary primary efficacy endpoint on the logit scale using data from Arms 2, 3, and 4 (JNJ-3989 at 200, 100, and 40 mg dose, respectively +NA), and Arm 6 (placebo+placebo+NA) as control. The “max trend test” is to test the null hypothesis that none of the doses is better than control (i.e. the flat dose response curve). The power to reject the null hypothesis is $\geq 85\%$ under all 5 candidate dose-response models for an absolute response rate of the highest dose of JNJ-3989 of at least 25% (one-sided alpha level of 5%). In addition, assuming a response rate of 5% in control Arm 6, the study sample size provides a statistical power $\geq 84\%$ to detect a difference of $\geq 20\%$ in the primary endpoint between Arm 1 and Arm 6, and power $\geq 76\%$ for at least a 20% delta between Arm 5 and Arm 6, using a fixed sequence approach for controlling for multiplicity.

The testing among the regimens (Arm 1, 3, and 5) will be performed using the min test approach control for the one-sided Type 1 error of 0.05. The chosen study sample size and randomization allocation provides acceptable power levels also for the comparison of different combination regimens, ie, JNJ-3989+JNJ-6379+NA (Arm 1, 100-mg dose of JNJ-3989) versus JNJ-3989+NA (Arm 3, 100-mg dose of JNJ-3989), and versus JNJ-6379+NA (Arm 5), respectively. For example, for the same delta of 25% between Arm 1 and Arm 3 and between Arm 1 and Arm 5, the power to conclude that Arm 1 is statistically superior to Arm 3 and Arm 5 is 87%, assuming a response rate of 25% in both Arm 3 and 5. Details are provided in Section 9 of the protocol Amendment 1.

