After a positive significant dose-response signal is established for the combination regimen JNJ-3989+NA, the testing procedure continues in a fixed sequence to control the type 1 error in presence of multiple testing, with the comparison of Arm 1 (JNJ-3989+JNJ-6379+NA) with control Arm 6 at a one-sided alpha of 0.05. If Arm 1 is found statistically superior to control Arm 6, then the combination regimen JNJ-6379+NA (Arm 5) is compared to control Arm 6 at 0.05 one-sided alpha level. The Mantel-Haenszel (MH) test (Mantel N. et al., 1959) for the difference of 2 proportions adjusted for the 2 randomization stratification factors (treatment history

status and screening HBeAg status) will be used at one-sided 0.05 alpha level in each of the above mentioned pairwise comparisons.

5.2.2.1.1.3. Scientific Question Part c: Comparisons Among Combination Regimens

For the regimen-finding objective, the statistical comparisons among the regimens (Arm 1, 3, and 5) will be performed using the min test approach to control for the Type I error rate at the one-sided 0.05 alpha level. The JNJ-3989+JNJ-6379+NA combination regimen will be declared statistically superior to the dual regimens if both tests of Arm 1 vs Arm 3 and Arm 1 vs Arm 5 demonstrate statistical significance at the one-sided 0.05 level. The Mantel-Haenszel test for the difference of 2 proportions adjusted for the 2 randomization stratification factors will be applied.

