For subjects HBeAg positive at screening: The model will include treatment, the 2 randomization factors and the available non-missing log-transformed HBV DNA, log-transformed HBeAg values, log-transformed ALT values and HBsAg (values < LLOQ, TND or TD will be first substituted following rules described in [Table 3](#)) for each scheduled time point (Week) and the following demographic and baseline characteristics ([King G. et al., & Honaker J. et al.](#)): age, gender, and baseline log value for HBV DNA level, baseline log HBsAg level, baseline HBeAg level, and baseline log ALT level.

For subjects HBeAg negative at screening: The model will include treatment, the 2 randomization factors and the available non-missing log-transformed HBV DNA, log-transformed ALT, and log-transformed HBsAg (values < LLOQ, TND or TD will be first substituted following rules described in [Table 3](#)) for each scheduled time point (Week) and the following demographic and baseline characteristics ([King G. et al., & Honaker J. et al.](#)): age, gender, and baseline log transformed value for HBV DNA level, baseline log HBsAg level and baseline log ALT level.

A total of 200 datasets (comprising both HBeAg positive and negative subjects at screening) will be generated where both intermittent and monotone missing ALT, HBV DNA, and/or HBsAg values will be imputed for each subject relying on non-missing data from all other subjects within the same treatment group. Once the 200 completed datasets are generated by filling in the missing data with samples from the imputation model, the primary endpoint response status (binary variable) will be derived using both imputed and observed ALT, HBV DNA, HBeAg, and HBsAg values at Week 44.

For the MCP-step, the max trend test will be obtained for each of the imputed datasets and the multiplicity adjusted p-value associated with the largest T-test statistic will be saved. All p-values will be transformed to a Z-test statistic using the inverse cumulative distribution function of the standard normal distribution. The resulting 200 Z-test statistics and their standard error of 1 will be combined into an overall Z test result, using SAS PROC MIANALYZE.

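### The primary-endpoint tests of Arm 1 vs Arm 3 and Arm 1 vs Arm 5 leave out baseline HBsAg, giving up roughly 4 to 9 points of min-test power at an assumed correlation of 0.5

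*SAP*

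**What the plan says.** **The test.** SAP 5.2.2.1.1.3 declares the triple regimen superior only if "both tests of Arm 1 vs Arm 3 and Arm 1 vs Arm 5 demonstrate statistical significance at the one-sided 0.05 level". For each comparison, "The Mantel-Haenszel test for the difference of 2 proportions adjusted for the 2 randomization stratification factors will be applied". Protocol 9.1 and 9.4.1.1 say the same.

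**The response.** SAP 5.2.1 builds it from four Week 44 laboratory results: ALT, HBV DNA, HBeAg, and HBsAg below 10 IU/mL.

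**The covariate.** Quantitative HBsAg is taken on Day 1 (protocol 1.3.1) and summarised on the log10 scale (SAP 4.2.2). Entry requires more than 100 IU/mL, with no upper limit (protocol 5.1, criterion 6).

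**Where baseline HBsAg is used.** It is in both imputation models (SAP 5.2.2.1.4); the model for participants HBeAg-negative at screening lists "baseline log transformed value for HBV DNA level, baseline log HBsAg level and baseline log ALT level". It also defines efficacy subgroups (SAP 2.4.1, modelled one variable at a time in 5.2.5) and is named for exploratory modelling in protocol 9.4.1.3.

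**Where it is not used.** It is absent from the min test and from the sensitivity estimators in SAP 5.2.2.2. The protocol's secondary comparison is made "in a logistic regression model with factors for treatment arm, treatment status and HBeAg status at screening".

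**Power.** Protocol 9.2 simulates an unadjusted two-proportion test and says that "the power levels vary depending on both the rate difference between Arm 1 and Arm 3 and the assumed rate for Arm 5". SAP 1.4 quotes 87% "for the same delta of 25% between Arm 1 and Arm 3 and between Arm 1 and Arm 5", with 25% response in Arms 3 and 5.

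**The concern.** A participant entering just above 100 IU/mL needs a fall of little more than log10(100/10) = 1 log10 to pass the HBsAg criterion. One in the SAP's top baseline band (10,000 IU/mL or more) needs at least log10(10,000/10) = 3. Baseline HBsAg is therefore a natural predictor of response, and the SAP treats it as one when it imputes missing values. Elsewhere the SAP adjusts for the baseline value as a matter of course: in the marker-change mixed model (5.4.5.1), the fibrosis ANCOVA (5.5.1) and the HBQOL ANCOVA (9.1). The statement in protocol 4.2 that two factors are the feasible maximum is about randomisation and does not limit the analysis model.

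At stake is the min test, which needs two wins, one of them against only 45 participants. Table 7 gives it a power of 0.423 at 40/25/25% and 0.680 at 45/25/25%. Explaining outcome variation with a covariate already in hand would raise that power at the same sample size and alpha.

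**Working it through.** Rates are written Arm 1/Arm 3/Arm 5.

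**1. Inputs.** n = 90, 90 and 45 (SAP 1.4). One-sided 0.05 for each test, both required (SAP 5.2.2.1.1.3). Rates from protocol Table 7. The correlation is in neither document and is assumed: 0.5, range 0.3 to 0.7.

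**2. The plan's own figure (50/25/25%), pooled z test.** Power = Φ((Δ − 1.645·SE0)/SE1), with SE0 pooled and SE1 unpooled.
- Arm 1 vs 3: pooled rate 0.375; SE0 = √(0.375×0.625×2/90) = 0.0722; SE1 = √((0.25+0.1875)/90) = 0.0697. Power = Φ((0.25−0.1187)/0.0697) = Φ(1.88) = 0.970.
- Arm 1 vs 5: pooled rate (45+11.25)/135 = 0.4167; SE0 = √(0.4167×0.5833×(1/90+1/45)) = 0.0900; SE1 = √(0.25/90+0.1875/45) = 0.0833. Power = Φ((0.25−0.1481)/0.0833) = Φ(1.22) = 0.889.
- Joint: sharing Arm 1 gives a correlation of (0.25/90)/(0.0697×0.0833) = 0.48, and the bivariate normal gives 0.873 (0.871 by simulation).

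Table 7 states 0.970, 0.889 and 0.871, so the plan's figures reproduce.

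**3. Variance formula.** Adjustment multiplies each variance by about 1 − r², where r is the correlation of the covariate with the binary response within arm. A latent correlation of 0.5 between baseline and Week 44 values becomes only about 0.40 in size once response is cut to yes/no, so the multiplier is 1 − 0.16 = 0.84. At r = 0.4 the headline row gains 5.2 points. If r itself were 0.5 (multiplier 0.75), power would go from 0.873 to 0.949, a gain of 7.7.

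**4. Patient-level simulation.** Response is a threshold on a latent normal variable, set to the Table 7 rates. Baseline is standard normal with latent correlation 0.5. There are four strata: 40% untreated, 40% of them HBeAg-positive (protocol 4.1), and 25% HBeAg-positive among the suppressed (assumed). Min-test power over 3,000 trials, where the adjusted test is a logistic model with the strata and baseline:

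| Rates | Table 7 | Stratified MH | Adjusted |
|---|---|---|---|
| 40/25/25% | 0.423 | 0.41 | 0.49 |
| 45/25/25% | 0.680 | 0.68 | 0.76 |
| 50/25/25% | 0.871 | 0.86 | 0.92 |

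Two repeat runs of 2,500 trials gave gains of 7 and 8, 8 and 9, and 5 and 5 points. At 45/25/10% the gain is about 4 to 5. For 45/25/25%, power goes from 0.66 to 0.69 at a correlation of 0.3 and from 0.67 to 0.84 at 0.7.

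**5. The same check with a linear-model risk difference.** Against an unadjusted risk difference with unpooled variance, latent 0.5 gives 0.456 to 0.521, 0.713 to 0.779 and 0.883 to 0.923: gains of 6.5, 6.7 and 4.0. These are a little lower because an unpooled comparator already starts above the MH test.

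**6. Type I error.** With all arms at 25%, each adjusted logistic comparison rejected in 0.042 to 0.057 of trials. At 25/25/10%, joint rejection with the adjusted risk difference was 0.049, against 0.048 unadjusted.

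**7. Which adjusted test.** With 45% and 25% in Arms 1 and 3, latent correlation 0.5 and 2,500 trials:

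| Arm 5 rate | Stratified MH | Logistic Wald | Adjusted risk difference or score test |
|---|---|---|---|
| 5% | 0.885 | 0.839 | 0.93 |
| 2% | 0.866 | 0.532 | 0.92 |

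With no responders in Arm 5 the log-odds ratio diverges and the Wald test cannot reject.

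**The case against.** The stratified MH test is prespecified, valid, and targets the stated summary, a difference in proportions (SAP 5.2.2). Adding a covariate is an efficiency preference in a Phase 2b trial. That stands, and it limits the point to efficiency.

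The correlation has no source, and at 0.3 the gain is only 2 to 3 points. That also stands. HBsAg is one of four criteria, and the simulation collapses them into one latent variable. The strata may already carry part of the information: in the variance-formula calculation with r = 0.5 overall, strata that explain a correlation of 0.2 to 0.4 leave a headline-row power of 0.941 to 0.908. That is a gain of about 7 to 3.5 points over 0.873.

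The gain also depends on the row. Where Arm 5 is at 10%, Table 7 already gives min-test power of 0.698, 0.882 and 0.972, and less can be won.

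The most serious objection is that the obvious adjusted analysis, a logistic model with a Wald test, can do harm. A low Arm 5 rate is plausible: protocol 2.2.1 reports no HBsAg change after 4 weeks of JNJ-6379 and no relevant mean change at 24 weeks on 75 mg, and protocol 9.2 assumes 5% for control. The SAP foresees zero response rates and uses Firth penalisation in MCP-Mod (5.2.2.1.1.1). This objection decides the form of the fix; it does not remove the point.

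**Conclusion.** The omission is real, and nothing else in the plan makes up for it in this test. The subgroup models are exploratory, use observed cases and sit outside the min test. At an assumed latent correlation of 0.5, the min-test power forgone is about 8 to 9 points at 40/25/25% and 45/25/25%, about 5 at 50/25/25% and 4 to 5 at 45/25/10%. At 45/25/25% it is about 3 points at a correlation of 0.3 and about 16 at 0.7. All of these shrink if HBeAg status and treatment history already explain part of baseline HBsAg.

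Three stronger readings might be inferred and are not supported:
- That the regimen comparison is the least powered primary hypothesis. Table 7 gives Arm 5 vs Arm 6 a power of only 0.196 to 0.200 when Arm 5 responds at 10%.
- That the planned test or its stated power is wrong. The test is valid, and the 87% reproduces.
- That the plan ignores baseline HBsAg. It uses it for imputation and for subgroups, but not in this test.

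**What to change.** In SAP 5.2.2.1.1.3, test Arm 1 vs 3 and Arm 1 vs 5 with a covariate-adjusted difference in proportions. The model contains arm, screening HBeAg status, treatment history and continuous baseline log10 HBsAg. The estimate can be a standardised (g-computation) or linear-model risk difference with a robust standard error; an adjusted score test is an alternative. Pool over imputations by Rubin's rules. Keep the stratified MH test as the sensitivity analysis. The min-test rule and the alpha do not change. Do not use an unpenalised logistic Wald test.

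The model has to be fixed before unblinding. The SAP's history for Amendment 2 (19 May 2022) mentions past interim analyses and an initial analysis of the data. SAP 3.1 places every interim analysis after the primary analysis, at which the sponsor is unblinded (SAP 1.5). If unblinding has occurred, as this suggests, the planned MH test stays primary and the adjusted analysis is added as a labelled supplementary estimator.

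The cost is SAP wording, slightly more programming and reliance on a working model. No new data are needed.

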5.2.2.1.2. Data Included

All available data from mITT analysis set, after taking into account all the intercurrent events and applying the intercurrent event strategies specified in Section [5.2.2](#), will be included.

5.2.2.1.3. Assumptions

- Missing Data for ALT, HBV DNA, and HBsAg are Missing at Random (MAR)
- The treatment effect is homogeneous across strata

5.2.2.1.4. Missing Data Handling Rule

Participants who withdraw from the study prior to Week 48 will be considered as non-responders.

If a participant remains in the study after experiencing a major protocol deviation (defined for the purpose of efficacy analyses and is an intercurrent event [ICE]) and has missing Week 44 lab value(s) (ALT, HBV DNA, HBeAg [screening positive participants] and HBsAg), then the imputation to non-response will be applied. If the value for the primary endpoint at Week 44 is available, then such data will be used to determine their response status.

For the participants still in the study at Week 48 or for participants that have neither discontinued treatment early nor experienced any major protocol violations (defined for the purpose of efficacy analyses and is an intercurrent event), and ALT, HBV DNA, HBeAg (screening positive participants) and/or HBsAg values missing at Week 44, then the primary method to handle missing data will be the Multiple Imputation (MI) approach ([Ratitch B. et al., 2013](#)) under the assumption of MAR will be applied in a joint multivariate fashion to leverage the correlation between ALT, HBV DNA, and HBsAg values over time.

The multiple imputation (MI) multivariate model will use all available data and be applied to the continuous ALT, HBV DNA, HBeAg (screening positive participants) and HBsAg values (not the binary endpoint). Of note, also the pre-ICE data for those subjects who experienced an ICE will be included in the MI model; but for these subjects the response status will be applied according to the ICE strategies before running the MI model.

If a subject is HBeAg negative at screening, s/he is considered HBeAg negative also at Week 48 for the purpose of determining the status of the primary efficacy endpoint. Because the quantitative HBeAg assessments are collected only for participants who are HBeAg positive at screening, two separate MI models are defined as follows:

For subjects HBeAg positive at screening: The model will include treatment, the 2 randomization factors and the available non-missing log-transformed HBV DNA, log-transformed HBeAg values, log-transformed ALT values and HBsAg (values < LLOQ, TND or TD will be first substituted following rules described in [Table 3](#)) for each scheduled time point (Week) and the following demographic and baseline characteristics ([King G. et al., & Honaker J. et al.](#)): age, gender, and baseline log value for HBV DNA level, baseline log HBsAg level, baseline HBeAg level, and baseline log ALT level.

For subjects HBeAg negative at screening: The model will include treatment, the 2 randomization factors and the available non-missing log-transformed HBV DNA, log-transformed ALT, and log-transformed HBsAg (values < LLOQ, TND or TD will be first substituted following rules described in [Table 3](#)) for each scheduled time point (Week) and the following demographic and baseline characteristics ([King G. et al., & Honaker J. et al.](#)): age, gender, and baseline log transformed value for HBV DNA level, baseline log HBsAg level and baseline log ALT level.

A total of 200 datasets (comprising both HBeAg positive and negative subjects at screening) will be generated where both intermittent and monotone missing ALT, HBV DNA, and/or HBsAg values will be imputed for each subject relying on non-missing data from all other subjects within the same treatment group. Once the 200 completed datasets are generated by filling in the missing data with samples from the imputation model, the primary endpoint response status (binary variable) will be derived using both imputed and observed ALT, HBV DNA, HBeAg, and HBsAg values at Week 44.

For the MCP-step, the max trend test will be obtained for each of the imputed datasets and the multiplicity adjusted p-value associated with the largest T-test statistic will be saved. All p-values will be transformed to a Z-test statistic using the inverse cumulative distribution function of the standard normal distribution. The resulting 200 Z-test statistics and their standard error of 1 will be combined into an overall Z test result, using SAS PROC MIANALYZE.

For Mod-step, model averaging techniques across all 5 candidate models will apply to each imputed dataset and produce the weighted estimates of the treatment effect across the JNJ-3989 dose range (0 mg to 200 mg). The standard errors will be obtained using bootstrapping techniques and then combined into one result using PROC MIANALYZE. The final response estimates on the logit scale for each dose level in the range 0 mg to 200 mg and their 90% CI will be back transformed to the original scale of proportion of responders and plotted with the corresponding 90% confidence band.

For pairwise comparisons of Arms 1 vs 6 and Arm 5 vs 6, as well as the comparisons amongst combination regimens (Arms 1, 3, and 5), the MH test will be performed for each dataset to generate individual estimates of the difference in proportions and the standard error adjusted on

stratification factors. Then the results from these multiple imputed datasets are combined (pooled) for obtaining the overall inference and p-value in a way that accounts for the variability between imputations (Ratitch B. et al., 2013)

Depending on the amount of missing data, the number of imputed datasets to be generated will be increased appropriately from the planned 200 to ensure robustness in the MI results and relative efficiency (Graham JW. et al., 2007).

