5.2. Primary Efficacy Endpoint

5.2.1. Definition

The primary efficacy endpoint is defined as the proportion of participants meeting the NA treatment completion criteria **at Week 48**.

A participant will be defined as responder in meeting the NA treatment completion criteria at Week 48, if the following criteria are met based on the clinical laboratory tests performed **at Week 44**:

- ALT <3x upper limit of normal (ULN), AND
- HBV DNA <LLOQ, AND
- HBeAg-negative (<LLOQ), AND
- HBsAg <10 IU/mL.

Note: In case of ALT elevation $\geq 3x$ ULN at Week 44, the ALT re-test before Week 48 may be performed. If the ALT re-test meets the criteria above, the participant will be considered as responder as satisfying the NA treatment completion criteria.

Note: Quantitative HBeAg assessment is only performed at Week 44 for participants who are HBeAg positive at screening. Therefore, if a participant is HBeAg negative at screening, they are assumed to be negative at Week 44 for the purpose of the primary endpoint.

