5.3.2.1.4. Missing Data Handling Rule

Participants who withdraw from the study prior to Week 72 will be considered as non-responders.

If a participant remains in the study after experiencing a major protocol deviation (defined for the purpose of efficacy analyses and is an intercurrent event) and has missing Week 72 value, then the imputation to non-response will be applied. If the value for the endpoint at Week 72 is available, then such data will be used to determine their response status.

For the participants still in the study at Week 72 or for participants that have neither discontinued treatment early nor experienced any major protocol violations (defined for the purpose of efficacy analyses and is an intercurrent event), and HBsAg values missing at Week 72, then the primary method to handle missing data will be the Multiple Imputation (MI) approach ([Ratitch B. et al., 2013](#)) under the assumption of MAR will be applied to a model for continuous HBsAg log values over time.

The MI model will use all available data and be applied to the continuous log-transformed HBsAg values (not the binary endpoint). Of note, also the pre-ICE data for those subjects who experienced an ICE will be included in the MI model; but for these subjects the response status will be applied according to the ICE strategies before running the MI model.

The model will include treatment, the 2 randomization factors and the available non-missing log-transformed HBsAg (values < LLOQ, TND or TD will be first substituted following rules described in [Table 3](#)) for each scheduled time point (Week) and the following demographic and baseline characteristics ([King G. et al., & Honaker J. et al.](#)): age, gender, and baseline log-transformed value for HBsAg level.

A total of 200 datasets will be generated where both intermittent and monotone missing HBsAg values will be imputed for each subject relying on non-missing data from all other subjects within the same treatment group. Once the 200 completed datasets are generated by filling in the missing data with samples from the imputation model, the key secondary endpoint response status (binary variable) will be derived using both imputed and observed HBsAg values at Week 72.

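### As written, the SAP's imputation model for HBeAg-positive participants leaves post-baseline HBsAg unlogged, unlike its two sister models: a real error with a small expected effect

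*SAP*

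**What the plan says.** Under SAP 5.2.2.1.4, participants still in the study who have a Week 44 marker missing, and who are not already set to non-response, are handled by multiple imputation. The method "will be applied in a joint multivariate fashion to leverage the correlation between ALT, HBV DNA, and HBsAg values over time". There are two models, split by HBeAg status at screening:

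- HBeAg-positive, post-baseline markers: "the available non-missing log-transformed HBV DNA, log-transformed HBeAg values, log-transformed ALT values and HBsAg".
- HBeAg-positive, baseline covariates include "baseline log HBsAg level, baseline HBeAg level, and baseline log ALT level".
- HBeAg-negative, post-baseline markers: "the available non-missing log-transformed HBV DNA, log-transformed ALT, and log-transformed HBsAg".

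The single model for the key secondary endpoint (SAP 5.3.2.1.4) is to "be applied to the continuous log-transformed HBsAg values (not the binary endpoint").

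After imputation, response status "will be derived using both imputed and observed ALT, HBV DNA, HBeAg, and HBsAg values at Week 44". The HBsAg part of the response rule in SAP 5.2.1 is "HBsAg <10 IU/mL", with no lower bound. The SAP gives no imputation distribution, no bounds or truncation, and no rule for impossible imputed values. The substitution in SAP Table 3 applies to observed values before imputation.

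**The concern.** The scale of HBsAg decides whether the imputation behaves sensibly. From the LLOQ of 0.05 to the undiluted upper limit of 124,925 IU/mL (SAP Table 3), HBsAg spans log10(124,925 / 0.05) = 6.4 log10 units. A normal model on the untransformed scale takes its residual spread from the largest values. For a participant with tens to thousands of IU/mL, many draws would then be negative. A negative HBsAg is impossible, but it satisfies the criterion. This could happen in any arm, including the control arm, which has no drug that lowers HBsAg.

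The text also leaves two programmers free to code different scales for the main analysis of the primary endpoint.

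**Working it through.** **Wording.** In the HBeAg-positive model the log label is attached separately to HBV DNA, HBeAg and ALT, but not to HBsAg. In the HBeAg-negative model it is attached to every marker, including HBsAg. The Week 72 model logs HBsAg, and the HBeAg-positive model logs its own baseline HBsAg. Baseline HBeAg is unlogged although post-baseline HBeAg is logged. The sentence is therefore inconsistent with itself and with both sister models.

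**Consequence.** The plan states no figure to reproduce here. The HBsAg distributions below are assumptions, because the documents give none. Both checks assume an untransformed scale and an unbounded normal model.

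*Check 1: a normal distribution matched to a log-normal HBsAg.* With s = SD(log10) x ln 10, the coefficient of variation is CV = sqrt(exp(s²) − 1), and P(draw < 0) = Φ(−1/CV), whatever the mean.

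- SD 0.5: CV = 1.66, P = 0.27
- SD 0.8: CV = 5.36, P = 0.43
- SD 1.0: CV = 14.1, P = 0.47

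With mean log10 of 3 and SD 0.8, P(draw < 10) is 0.426, against a true Φ((1 − 3)/0.8) = 0.006.

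*Check 2: conditioning on earlier visits.* I simulated Week 44 HBsAg imputed by a normal regression draw from log baseline, Week 36 and Week 40 (2,000 runs per row). Assumptions on log10: baseline mean 4, SD 0.6; SD of decline 0.6; visit error SD 0.08. A false draw is one below 10 IU/mL when the true value is at least 10. Results for n = 30:

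| Mean log10 at Week 44 | Untransformed: P(<0) | Untransformed: P(<10) | Log scale: P(<10) | True P(<10) | Untransformed: P(false) |
|---|---|---|---|---|---|
| 1.5 | 0.230 | 0.284 | 0.280 | 0.278 | 0.131 |
| 2.0 | 0.220 | 0.244 | 0.106 | 0.103 | 0.193 |
| 2.5 | 0.226 | 0.232 | 0.034 | 0.036 | 0.218 |
| 3.0 | 0.212 | 0.214 | 0.011 | 0.010 | 0.211 |
| 3.9 (control-like) | 0.214 | 0.214 | 0.000 | 0.000 | 0.214 |

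With n = 15 the false share runs from 0.128 to 0.208. On the log scale the imputed share tracks the truth throughout. Where the true mean is close to the threshold (first row), errors in both directions nearly cancel: 0.284 against 0.278. The net excess is largest where HBsAg is high.

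**Size on the endpoint.** Expected false responders per arm = HBeAg-positive participants x share with Week 44 HBsAg imputed x false share x P(other three criteria met).

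- *HBeAg-positive participants.* Protocol 4.1 aims for 40% not currently treated, of whom 40% are expected to be HBeAg-positive: 450 x 0.40 x 0.40 = 72, or 90 x 0.16 = 14.4 per 90-participant arm. The number of virologically suppressed HBeAg-positive participants is not given, so I used 30 per arm as an assumed upper case.
- *Share imputed.* 5% and 10%, assumed.
- *Other three criteria met.* 0.05 to 0.30, assumed.

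Lower case: 14.4 x 0.05 x 0.2 x 0.05 = 0.007, and with 0.30 in the last place, 0.04. Upper case: 30 x 0.10 x 0.21 x 0.30 = 0.19 participants, and 0.19 / 90 = 0.2 percentage points of the arm's response rate.

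**The case against.** A reader might infer that the SAP chose to analyse HBsAg in IU/mL. It does not say so. Neither a unit nor the absence of transformation is stated for this variable, and the final phrase of the list can be read as one log label covering both ALT and HBsAg. With both sister models logged and a second log missing from the same sentence, a drafting slip is the likelier explanation. This stands as an account of the origin. It does not settle how the text should be coded, because elsewhere the label is repeated marker by marker.

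A reader might also infer that the primary result will contain false responders in numbers that matter. The documents do not support that either, for four reasons:

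- The unbounded normal model is an inference from silence. The SAP says only that the imputation is joint and multivariate.
- A low HBsAg draw is one of four criteria. HBeAg below LLOQ is a real hurdle for participants who were HBeAg-positive at screening.
- Few participants are imputed. Withdrawal before Week 48, discontinuation before Week 44, and intercurrent-event deviations with missing data all count as non-response. The mITT set (SAP 2.3) also removes participants whose primary assessment was lost to the pandemic.
- The LOCF, tipping-point, missing-as-non-response and per-protocol analyses (SAP 5.2.2.2.2, 5.2.2.2.3, 5.2.3 and 5.2.4) do not use this model, so a large distortion would show against them.

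These points limit the size. They do not remove the problem. HBsAg can be the only missing marker, and then the draw alone decides response when the other three criteria are met. The supplementary ITT analysis (SAP 5.2.2.3.1) reuses the same imputation rule and restores the pandemic-affected participants, so its exposure is wider.

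**Conclusion.** Wrong as written, minor. The inconsistency is in the current text of an operative rule for the primary endpoint's main estimator. If that rule is coded literally with an unbounded normal model, roughly a fifth of imputed Week 44 HBsAg values in HBeAg-positive participants would be falsely below 10 IU/mL; on the log scale the imputed share matches the truth. The expected effect on the endpoint is about 0.01 to 0.2 false responders per 90-participant arm, which is unlikely to change a conclusion.

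Confidence is high on the wording and the mechanism. The size rests on assumed HBsAg distributions, missing-data rates and chances of meeting the other criteria. The documents do not show which scale was coded.

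**What to change.** In the HBeAg-positive model of SAP 5.2.2.1.4:

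- State that post-baseline HBsAg is log-transformed at every scheduled visit, and that baseline HBeAg is logged.
- Name the imputation distribution and any bounds, for both models.
- State that imputed values are back-transformed before the response thresholds are applied.

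SAP Amendment 2 refers to past interim analyses and to an initial analysis of the data. The sponsor should therefore also confirm and document which scale the executed code used. If HBsAg was left untransformed, the primary and ITT imputation analyses should be rerun on the log scale.

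The cost is a line or two of SAP text and a code check. Design, sample size and data collection are unaffected.
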